4.6. Planned Analyses

The primary analysis will be performed after all randomized patients have completed the Month 6 visit or discontinued from the study. For the primary analysis, as this study will be ongoing with some patients in the 9-Month Treatment Extension Period, the study database will be locked with all data up to a prespecified cutoff date quality controlled, ie, data in the EDC system will be cleaned and frozen and external laboratory data will be cleaned and quality controlled (and quality assured, where appropriate).

The primary analysis will include data on or prior to this prespecified cutoff date. For the efficacy summaries, all data up to and including the Month 6 visit will be presented. For assessments with start and end dates (eg, AEs, medications), the start date will be compared with the pre-specified cutoff date. Data records with start dates after the specified data cutoff date will be excluded.

The final analysis will be conducted after all patients have completed the Month 15 visit or discontinued from the study. The database will undergo a final lock.

Additional details regarding the database lock process are located in the study Data Management Plan.

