5.7.3.1. Kidney Stone Events

CT scans for radiographic kidney stone events are read in pairs blinded to visit date (baseline and Month 15). All kidney stone-related analyses in this section will be done with all data collected.

A clinical kidney stone event is defined as one of the following:

- Visible passage of a kidney stone
- A procedural intervention for removal of an asymptomatic or symptomatic stone (information on the location, number, and size of stones removed will be collected)
- Or, in the case of potential stone passages without visible stones, it will be up to the Investigator to evaluate patients' symptoms and determine whether a stone passage occurred or the symptoms were due to a different cause.

A radiographic kidney stone event is defined as a kidney stone that is increased in size by $\geq 2 \text{ mm}$ in at least one dimension or a new stone ($\geq 1 \text{ mm}$ in size) observed on CT at Month 15 relative to baseline.

Time to first kidney stone event

Time to first event is defined as date of the first study drug to the first date of a kidney stone event. Censoring applies to patients who do not have a kidney stone event during the study. The follow-up time of these patients will be censored at the lost to follow-up date, study discontinuation, data cut-off date, or end of study, whichever occurs first.

Time to the first kidney stone event will be analyzed for a combination of both clinical and radiographic kidney stone events and for clinical kidney stone events separately for both the 6-month primary analysis period and the 15-month DB period (FA). All available data at the time of each database lock will be used. Kaplan-Meier estimator will be used to estimate the distribution of time to first kidney stone event in each treatment group. A log-rank test will be used to evaluate the treatment differences between each dose and the placebo. In addition, Cox proportional hazard regression will be performed to estimate the hazard ratio along with the 95% CI and p-value for each dose compared to the placebo. The model includes treatment, number of historical kidney stone events (>1 versus \leq 1) in the 12 months prior to screening.

Incidence rate of clinical and radiological kidney stone events

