The incidence rate of kidney stone events will be analyzed for a combination of both clinical and radiographic kidney stone events and for clinical kidney stone events separately for both the 6-month primary analysis period and the 15-month DB period (FA).

The incidence rate will be calculated as the total number of kidney stone events divided by total person-years at risk during the respective period (ie, 6-month primary analysis period and 15-month DB period). Years at risk is defined as (time from first lumasiran dose until 168 days after the last dose of lumasiran, lost to follow-up date, study discontinuation, data cut-off date, or end of study, whichever occurs first)/365.25.

The endpoint will be analyzed using a negative binomial regression model that include fixed effects of the treatment arm and the number of historical kidney stone events (>1 versus \leq 1) in the 12 months prior to screening. The logarithm of the follow-up time of each patient will be included in the model as an offset variable. The p value and the ratio of mean kidney stone event rate between two treatment arms with the corresponding 95% CI will be estimated.

The total number of patients with at least one kidney stone event, total number of kidney stone events, total number of person-years will be presented. Descriptive statistics for the median and interquartile range of the kidney stone event rate will also be presented by treatment arm.

Other radiographic assessments

Change from baseline in radiographic assessments of kidney stones (eg stone volume) will be summarized descriptively.

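### The stone analyses at the primary lock are labelled as covering the 6-month period, but SAP 5.7.3.1 sets no Month 6 end for events or time at risk, and its combined 6-month analysis has no scheduled CT to draw on

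*SAP*

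**What the plan says.** SAP 5.7.3 opens by placing the exploratory endpoints within the 6-month primary analysis period, with a second summary over the 15-month double-blind period. SAP 5.7.3.1 repeats that split for both stone endpoints, each to be run on clinical events alone and on clinical and radiographic events combined.

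The data rules in the same section do not follow the split:

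- A blanket rule for the section: "All kidney stone-related analyses in this section will be done with all data collected".
- For time to first event: "All available data at the time of each database lock will be used". Patients without an event are "censored at the lost to follow-up date, study discontinuation, data cut-off date, or end of study, whichever occurs first". Month 6 is not in that list.
- For the incidence rate, the denominator is described as "total person-years at risk during the respective period". The formula for years at risk that follows stops at 168 days after the last dose, loss to follow-up, discontinuation, data cut-off or end of study. Month 6 is absent here too.

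SAP 4.6 sets the timing: "The primary analysis will be performed after all randomized patients have completed the Month 6 visit or discontinued from the study". It describes the trial at that point "as this study will be ongoing with some patients in the 9-Month Treatment Extension Period". It also states: "For the efficacy summaries, all data up to and including the Month 6 visit will be presented". Protocol 6.2.2 classes stone events as an efficacy assessment.

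SAP 5.7.3.1 defines a radiographic event by comparing the Month 15 CT with baseline. Protocol 6.2.2.2 makes both scans optional and allows a scan at early termination only after Month 6.

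**The concern.** The primary lock waits for the last patient's Month 6 visit, so with any staggered enrolment the earlier patients will have been followed for longer. Under the stated rules that extra follow-up enters the log-rank test, the Cox model and the negative binomial rate, all under a 6-month label. A programmer working from the period label, or from the Month 6 sentence in SAP 4.6, would produce different results from one working from the data rule in 5.7.3.1. Both could claim to have followed the SAP.

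The period also matters for interpretation. Protocol 3.3 says Month 9 dosing will help separate the effects of 3-monthly and 6-monthly dosing. Follow-up after Month 6 lies in the longer dosing interval, so a hazard ratio labelled as 6-month would blend the two.

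The combined analysis raises a separate difficulty: no scheduled post-baseline CT falls within the first six months.

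**Working it through.** The documents give no event count, event rate or power for the stone endpoints, so there is no figure of the plan's own to reproduce. The power table in SAP 2.6 concerns urinary oxalate only.

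**Inputs from the documents.** Month 3 is Day 85, Month 6 is Day 169 (±14), Month 9 is Day 253 (±28) and Month 15 is Day 421 (±28) (Protocol Table 1). Planned enrolment is 120 (SAP 2.6).

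**Assumptions.** Accrual is uniform over A days. There is no dropout and no missed dose. The cut-off falls when the last patient reaches Day 169. First clinical events occur at a constant 0.2, 0.5 or 1.0 per patient-year. One month is 30.44 days.

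**Step 1: does the rate formula stop at Month 6?** After the Month 3 dose the 168-day limit falls on Day 85 + 168 = 253, which is 84 days past Day 169. After the Month 9 dose it falls on Day 253 + 168 = 421. It never stops a fully dosed patient at Month 6.

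**Step 2: share of follow-up after Day 169.** A patient enrolled u days before the last one has min(169 + u, 421) days of follow-up, and by Step 1 the same time at risk for the rate. The interval from Month 6 to Month 15 is 421 − 169 = 252 days. The mean is 169 + A/2 when A ≤ 252, and 421 − 252²/(2A) otherwise. The share after Day 169 is 1 − 169/mean. The share reaching Day 421 is max(0, 1 − 252/A).

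| Assumed accrual | Mean follow-up (days) | After Day 169 | Reached Day 421 |
|---|---|---|---|
| 6 months (A = 182.6) | 169 + 91.3 = 260 | 35% | 0% |
| 12 months (A = 365.3) | 421 − 86.9 = 334 | 49% | 31% (about 37 of 120) |
| 18 months (A = 547.9) | 421 − 58.0 = 363 | 53% | 54% (about 65 of 120) |

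At 3 and 24 months of accrual the share after Day 169 is 21% and 55%.

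**Step 3: first events.** A patient leaves the risk set at the first event, so the share of first events after Day 169 is somewhat smaller than the share of follow-up. Expected first events by Day 169 are 120 × (1 − exp(−λ × 169/365.25)). The count to the cut-off averages the same expression over each patient's follow-up. With 12 months of accrual:

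| Rate λ per year | By Day 169 | To cut-off | Share after Day 169 |
|---|---|---|---|
| 0.2 | 10.6 | 20.0 | 47% |
| 0.5 | 24.8 | 43.5 | 43% |
| 1.0 | 44.4 | 70.6 | 37% |

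**Step 4: radiographic events.** For any Month 15 CT to precede the cut-off, accrual must exceed about 252 days, or 252/30.44 = 8.3 months. With the visit windows this ranges from 393 − 183 = 210 to 449 − 155 = 294 days. Below that, the combined 6-month analysis reproduces the clinical-only one, apart from any early-termination scan after Month 6, which the SAP definition does not mention. Above it, CT events can come only from patients who enrolled early, chose to be scanned and have a baseline scan. The Day 421 shares in Step 2 are therefore upper bounds on patients scanned.

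**The case against.** Analysing all follow-up to a data cut-off is a standard time-to-event convention, and the SAP states it openly. The endpoint is exploratory, no stated decision depends on it, and a complete 15-month analysis follows. The blanket all-data rule may mean only that stone analyses carry no medication exclusions, unlike the supersaturation analysis in SAP 5.7.2. Relabelling the table would remove the mismatch without discarding information.

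Several of these objections stand, and they rule out stronger readings that a reader might infer:

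- *That the 6-month Kaplan-Meier estimate is distorted.* It is not. An estimate at time t uses only risk sets and events up to t, so later follow-up extends the curve and leaves it unchanged through Day 169.
- *That the treatment comparison is biased.* Censoring at a calendar cut-off does not by itself bias the log-rank test or Cox model, and dependence on enrolment date is shared across randomised arms. The third dose is planned treatment, not contamination.
- *That Month 15 CT findings will enter.* This depends on an accrual length the documents do not give and on optional paired scans.
- *That SAP 4.6 is plainly contradicted.* The same section compares assessments with start and end dates against the cut-off date. If stone events belong there, the conflict with its Month 6 sentence weakens.
- *That the two stone tables must use different event sets.* The years-at-risk formula also lacks a Month 6 stop, so both may overrun alike.

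The remaining objections do not remove the point. The SAP does not say that its period label overrides its data rule, or that all data means only no medication exclusions. The conflict with the 6-month framing in 5.7.3 and with the rate's own period wording remains on any reading of 4.6. Relabelling alone would leave no analysis that matches the stated period, and would not give the combined 6-month analysis any content of its own.

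**Conclusion.** The point holds as an inconsistency of definition. Followed literally, SAP 5.7.3.1 yields a log-rank test, hazard ratio and incidence rate that carry a 6-month label but include later experience. Under uniform accrual over 6 to 18 months with no dropout, that is 35% to 53% of follow-up. Some inclusion follows from the text for any staggered enrolment; its size rests on the assumed accrual.

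The combined 6-month analysis is unsatisfactory either way. It is redundant if no Month 15 CT precedes the cut-off, and its radiographic ascertainment depends on enrolment date if one does. The documents do not support a claim of bias between arms or of an altered Kaplan-Meier estimate at Month 6. The consequence is mislabelled exploratory results and room for choice about the event window, which should be closed before the primary lock.

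**What to change.** In SAP 5.7.3.1, state that for the 6-month analyses both event counting and time at risk end at the Month 6 visit, or at Day 169 if there is no visit, unless an existing stopping reason comes first. Apply the same end date to time to first event and to the incidence rate, including its years-at-risk formula. Report clinical events only for this period. Keep the combined clinical-plus-radiographic analysis, using all data, for the 15-month final analysis. Say in SAP 4.6 which rule governs stone events at the primary lock.

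If an all-data analysis is also wanted at that lock, label it as running through the data cut-off and treat it as supplementary.

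The cost is a wording change and one censoring date. The downside is fewer events at the primary lock: on the assumed 0.5 events per year and 12-month accrual, about 25 first events instead of about 44. The later events are not lost, because they enter the final analysis.

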2.4. Randomization Methodology

Patients will be randomized 1:1:1 to receive lumasiran 284 mg, lumasiran 567 mg, or placebo in a DB manner. Stratification will be performed at randomization according to baseline urinary oxalate level ($\leq 1.25 \times ULN \text{ vs} > 1.25 \times ULN$) from the mean of the first 2 valid 24-hour urine collections and the number of historical kidney stone events in the 12 months prior to screening ($\leq 1 \text{ vs} > 1$).

For stratification, a historical kidney stone event is defined as:

- the visible passage of a kidney stone
- a procedural intervention for removal of an asymptomatic or symptomatic stone

- if more than 1 stone was removed in a given procedure, this counts as 1 event unless bilateral ureteral stones were removed, in which case this counts as 2 events
- if more than 1 procedure was required to remove a single stone, this counts as 1 event
- a new (≥1 mm) or enlarged (by ≥2 mm) kidney stone on computed tomography (CT) imaging
 - it must be evident from the CT scans that the new or enlarged kidney stone event occurred during the 12 months prior to screening
 - if a procedure was performed to remove the stone(s) identified by CT, then only the procedure will be counted to avoid double counting the same stone.

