4.5. Randomization Stratification Factors

The baseline urinary oxalate level ($\leq 1.25 \times ULN \text{ vs} > 1.25 \times ULN$) from the mean of the first 2 valid 24-hour urine collections and the number of historical kidney stone events in the 12 months prior to screening ($\leq 1 \text{ vs} > 1$) will be used as stratification factors. These stratification factors are recorded in both the IRT and the clinical database. In statistical analyses that use randomization stratification factors as covariates, the stratum assignment will reflect the values as recorded in the clinical database (EDC). In the presence of stratification errors, the stratification used in analysis may not match that in the IRT. A comparison of the number and percentage of patients in each randomization stratification factor in IRT versus the clinical database will be summarized by randomized treatment arm and overall.

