5.7.1.2. Primary Analysis

The hypothesis testing for the primary endpoint will be tested comparing each lumasiran group to the placebo group during the 6-month primary analysis period in the FAS with a 2-sided significance level of 0.05.

The primary endpoint will be analyzed using an MMRM approach using the ICE strategy described in Table 2. The outcome variable is percent change from baseline in 24-hour urinary oxalate to Month 6. The model includes baseline 24-hour urinary oxalate (as defined in Section 4.4) and the stratification factor of number of historical kidney stone events (≤ 1 versus >1 event in the 12 months prior to screening) as covariates, and fixed effect terms including treatment arm (lumasiran 567 mg or lumasiran 284 mg vs placebo), visit (Months 3, 4, 5, 6) and treatment-by-visit interaction. The primary treatment effect estimate from this model will represent the average percent change from baseline in 24-hour urinary oxalate across months 4 through 6, which is calculated via a linear contrast of the corresponding coefficients from the MMRM model. An unstructured covariance structure matrix fails to converge, then the following covariance structure will be assessed in this order: autoregressive (1), compound symmetry, Toeplitz. The Satterthwaite approximation will be used to estimate the denominator degrees of freedom.

The LS mean, standard error of the mean (SEM), 95% confidence interval (CI), and p-value will be generated for each treatment arm and the treatment difference between each lumasiran dose

and placebo from Months 4 through 6. In addition, the LS means, SEM, and 95% CI will also be generated for each visit (Months 3, 4, 5, 6) by treatment arm.

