5.7.2. Secondary Endpoints

The percentage of patients who achieve a $\geq 20\%$ reduction in 24-hour urinary oxalate from baseline to Month 6 (average across Months 4 through 6) will be analyzed using the Cochran-Mantel-Haenszel (CMH) test stratified by the 2 stratification factors (Section 4.5). The odds ratio with the corresponding 95% CI and associated p-value will be presented. In addition, the differences in proportion of responders and corresponding 95% CI using the Newcombe method based on the Wilson score will also be presented. In addition, a tabulation and a bar chart showing the proportion of patients with a $\geq 20\%$ reduction in 24-hour urinary oxalate from baseline to each visit and on average across Months 4 through 6 will be presented.

For the analysis of urinary calcium oxalate, selected medication could potentially impact the endpoint, therefore the assessments will be excluded from analysis if patients start, stop, or change any of the following medications within a specified time frame of the data collection:

- Vitamin C equivalent to ≥500 mg in a single day is taken at any point within 4 days prior to the start of or during the urine collection (see Table 2)
- The patient is on a new daily dose (relative to screening) of hydrochlorothiazide, allopurinol, topiramate, acetazolamide or furosemide at any point within 4 days prior to the start of or during the collection
- Urine alkalinization agents (potassium citrate, potassium citrate-citric acid, sodium citrate-citric acid, sodium citrate-potassium citrate-citric acid, sodium bicarbonate, potassium bicarbonate, or potassium bicarbonate-potassium citrate) started, stopped, or changed at any point within 2 days prior to the start of or during the collection (relative to screening)

Percent change in urinary calcium oxalate supersaturation from baseline to Month 6 (average across Months 4 through 6) will be analyzed using the same MMRM approach as for the primary endpoint. Descriptive statistics will also be generated for the actual values, change from baseline, and percent change from baseline at each scheduled visit by treatment arm. LS Mean (+/- SEM)

figures of percent reduction by treatment arm will be plotted as well as individual spaghetti plots. Listings will also be generated.

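### The log-rank test for time to first stone event names no strata, although randomisation and both stone-event models use stone history: a free, minor improvement to an exploratory analysis

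*SAP*

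**What the plan says.** SAP 5.7.3.1 plans Kaplan-Meier curves for time to first stone event and then a test: "A log-rank test will be used to evaluate the treatment differences between each dose and the placebo". No strata are given. The Cox model that follows is adjusted: "The model includes treatment, number of historical kidney stone events", split at >1 versus ≤1 in the 12 months before screening. The negative binomial model for the event rate has "fixed effects of the treatment arm and the number of historical kidney stone events", with the same split. Both endpoints are analysed at 6 and at 15 months.

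SAP 2.4 sets two randomisation factors: "Stratification will be performed at randomization according to baseline urinary oxalate level" (cut at 1.25 × ULN) and the number of stone events in the previous 12 months. SAP 4.5 adds: "These stratification factors are recorded in both the IRT and the clinical database". Where the SAP wants a stratified test it says so; for the responder endpoint in SAP 5.7.2 it specifies a Cochran-Mantel-Haenszel "test stratified by the 2 stratification factors (Section 4.5"). Silence in 5.7.3.1 is therefore fairly read as unstratified.

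Time to first stone event is listed as exploratory (SAP 2.2.2.3), and no multiplicity adjustment is planned (SAP 4.2).

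**The concern.** The sponsor treats stone history as important enough to randomise by it and to keep it in both stone-event models and in the primary model, yet omits it from one of the three stone-event tests. SAP 5.7.3.1 and the list of changes in SAP 6 give no reason.

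Stratified randomisation makes the arms alike on history. A crude log-rank test ignores that balance. Its variance still counts the spread between low-risk and high-risk patients, so the test rejects too rarely under the null. Under a real effect, the pooled treatment contrast is also diluted, because high-risk patients leave the placebo risk set fastest. What is at stake is some power in a small exploratory comparison, and a log-rank and a Cox p-value for the same contrast that rest on different adjustment.

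**Working it through.** **Inputs from the documents.** 1:1:1 allocation, 40 per arm, so 80 patients per comparison with placebo; two binary randomisation factors; Month 15 visit at day 421 ± 28. The only power figure in the plan is for the primary endpoint, and it reproduces: 30 / (45 × √(2/40)) = 2.981, and Φ(2.981 − 1.960) = 84.65% (83.8% with the noncentral t), against 84% stated. It does not bear on stone events, for which the documents give no rate, hazard ratio or power.

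**Assumed inputs.** Placebo rate 0.5 per year; treatment HR 0.5; 35% of patients with >1 prior event; stratum HRs as shown in the table.

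**Scale.** With no prognostic factor, expected first clinical events by day 421 are:

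- placebo: 40 × (1 − e^(−0.5 × 421/365.25)) = 17.5
- lumasiran: 40 × (1 − e^(−0.25 × 421/365.25)) = 10.0
- total: 27.5

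Schoenfeld's formula gives power Φ(√(27.5/4) × ln 2 − 1.96) = Φ(−0.14), about 44%. The simulated value is 43.8%.

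**Tests compared.** The crude test uses U²/V, where U is observed minus expected events in one arm and V is its hypergeometric variance. The stratified test uses (ΣU_s)²/ΣV_s over the two history strata. Both reject at |z| > 1.96.

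**Main results.** Clinical events, 15 months, 10,000 simulated trials per row, permuted blocks within the four randomisation strata (Monte Carlo SE up to 0.5 points for power and about 0.2 for the null rate; paired SE of the gain up to 0.3):

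| Stratum HR, history / oxalate | Power crude | Power by history | Gain | Null rate crude | Null rate by history |
|---|---|---|---|---|---|
| none | 43.8% | 43.8% | 0.0 | 5.0% | 5.0% |
| 2 / 1.2 | 40.5% | 42.2% | 1.7 | 4.5% | 5.0% |
| 2 / 1.5 | 39.6% | 41.0% | 1.4 | 4.4% | 4.9% |
| 3 / 2 | 33.3% | 36.8% | 3.5 | 3.4% | 4.8% |

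**Checks with simpler assumptions.**

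- History as the only prognostic factor, 5,000 trials: 40.6 to 42.2% at HR 2 (gain 1.6) and 36.6 to 40.0% at HR 3 (gain 3.4). The null rate at HR 3 moves from 3.5 to 4.9%. The cost if history is not prognostic is 0.1 to 0.5 points.
- Two binary factors, 6,000 trials: gains of 0.0 (42.3 to 42.3%), 1.7 (39.3 to 41.0%, HRs 2/1.5) and 4.3 (35.3 to 39.6%, HRs 3/2).

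**Sensitivity.**

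- At 6 months (168 days, about 12 events) history adds 0.4 to 1.1 points.
- If only 15% of patients have >1 prior event, it adds 0.7 points (HRs 2/1.5) or 2.4 (3/2) at 15 months.
- Combined endpoint, where a radiographic event is one "observed on CT at Month 15 relative to baseline" and so is dated to that visit (assumed CT uptake 50% or 100%): gains of 1.8 and 3.9 points at 50% uptake (44.4 to 46.2%; 37.2 to 41.1%) and 1.4 and 4.4 at 100% (49.8 to 51.2%; 41.3 to 45.7%). The cost if not prognostic is 0.3 to 0.5 points.
- Gains grow with the event rate. With 0.4 per year in the low-risk stratum, a stratum HR of 3, 25% or 40% of patients at high risk and 1.25 years of follow-up, power goes from 42.6 to 47.8% and from 46.0 to 52.8%. These correspond to average placebo rates of 0.4 × (0.75 + 0.25 × 3) = 0.6 and 0.4 × (0.60 + 0.40 × 3) = 0.72 per year.

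**Against the Cox test already planned.** In the three prognostic rows of the table, the history-adjusted Cox test has power of 40.8, 39.5 and 35.2%. The log-rank test by history exceeds it by 42.2 − 40.8 = 1.4, 41.0 − 39.5 = 1.5 and 36.8 − 35.2 = 1.6 points.

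**The case against.** The strongest reply is that nothing needs repair. An unstratified log-rank test is valid after stratified randomisation, and SAP 4.5 only fixes which data source is used when the factors enter as covariates. A crude test also sits naturally beside crude Kaplan-Meier curves, and the next sentences supply an adjusted hazard ratio, interval and p-value. Measured against that Cox test the gain is about 1.5 points, on power of roughly 35 to 42%. The two p-values would still differ after the change, because one is a score-type test and the other comes from a fitted model. The 35% share is unsupported: eligibility requires only one stone event in 5 years.

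All of that stands, and it is why the point is minor. It does not give a reason to leave out a factor that the trial already randomises by and that both neighbouring models include.

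Two stronger readings are tempting. One is that the omission is an error that threatens false positives; the null rates above are at or below 5%, so the opposite is true. The other is that baseline oxalate should also be used, as strata or as a covariate, since it is a randomisation factor absent from all three stone-event analyses. The documents do not support asking for that. Protocol 1.3 says stone risk rises with urinary oxalate but gives no size, and every patient already exceeds 40 mg/24 h (Protocol 4.1). Oxalate strata on top of history change power by −0.6 to +1.1 points. At 6 months the smallest of four strata has 2 or fewer events in 88 to 95% of simulated trials, against 9 to 19% with two strata. Part of the gain from oxalate as a covariate reflects a null rejection rate 0.1 to 0.7 points higher.

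**Conclusion.** The point holds as a free improvement to an exploratory analysis, not as an error or a contradiction. If stone history is prognostic with a stratum HR of 2 to 3, stratifying the log-rank test by it adds about 1 to 4 points of power at 15 months and brings a conservative null rate (3.4 to 4.5%) back to about 5%. If history is not prognostic, the cost is at most about 0.5 points.

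These figures assume a placebo rate of 0.5 per year, a treatment HR of 0.5 and 35% of patients with >1 prior event, none of which the documents state. The gain is smaller at 6 months or if few patients have >1 prior event, and larger at higher event rates. A reader might infer a large loss, since an assumed stratum HR of 5 gives 9 to 19 points, but nothing in the documents supports so strong an effect. Power stays low at the lower event rates either way, and the adjusted Cox model already covers much of the benefit.

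**What to change.** Add one phrase to the log-rank sentence in SAP 5.7.3.1: *stratified by stone history (≤1 vs >1 events in the year before screening), clinical database value, at the 6-month and the 15-month analysis*. Name the data source explicitly, because the rule in SAP 4.5 is worded for factors used as covariates, not as strata. Use history alone; no oxalate strata and no change to the Cox or negative binomial models are needed.

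The variable is already collected and the sample size is unaffected. The statistical cost is at most about 0.5 points of power if history does not predict events. If the sponsor prefers a crude test to accompany the Kaplan-Meier curves, one sentence saying so and naming the Cox result as the main inference would settle the mismatch.
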